#### **14.3 Treatment Compliance**

The prescribed dosage, timing, and mode of administration of study medication may not be changed except for PEG/RIG dosing as the subject's disease progresses. Drug compliance should be assessed on a per cycle basis by site staff either via phone calls or during their on-site study visits to assess their dosing compliance. Subjects will be asked questions regarding the compliance, and any departures from the intended regimen must be recorded in the eCRF. Study drug accountability and treatment compliance will be documented throughout the study period.

Subjects will be asked to return all unused medication including empty and partially used medication. Study medication dispensed at the previous visit will be collected by the site and compliance will be assessed by counting the returned study medication bottles.

Non-compliance is defined as taking <80% or >120% of study medication during evaluation periods (visit to visit).

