8.4.1.4. Exposure to Study Medication and Compliance

Exposure

Study medication exposure in days during MT-1186-A03 will be calculated for each subject using the following:

Actual exposure duration (days)

$$= \sum_{i=1}^{24} (\#count of planned study medication dosing days in cycle i - \#count of study medication days missed in cycle i + \#count of additional study medication days taken in cycle i)$$

The #count of planned study medication dosing is 10 in cycle 1 to 24.

The #count of study medication missed and additional study medication are collected by CRF visit.

The cycle will be automatically calculated using the date of the first dose in MT-1186-A03.

The total exposure in person years will be calculated as the sum of duration of exposure to study treatment over all patients in days divided by 365.25.

Treatment Compliance

Treatment compliance during MT-1186-A03 will be calculated for each subject using the following:

Treatment compliance(%)

$$= \frac{\text{Actual exposure duration}}{\sum_{i=1}^{24} (\#count of planned study medication dosing days in cycle i)} \times 100\%$$

Treatment compliance will be calculated using the formula above and reported to 1dp.

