9.1.6. Study Medication Exposure and Compliance

Study medication exposure during MT-1186-A03 will be calculated as specified in section 8.4.1.4. The following information will be summarized and listed for the safety analysis population:

- The number of subjects exposed to study treatment
- The number of subjects exposed to study treatment by oral administration
- The number of subjects exposed to study treatment by PEG/RIG administration
- Duration of exposure of study treatment (days) by Cycle and Total
- Total duration of exposure to study treatment, expressed as person years (sum of exposure to study treatment)
- Total duration of exposure (days) under PEG/RIG administration
- Time to date subjects switched to PEG/RIG administration

Treatment compliance will be determined by performing study treatment accountability of returned study treatment used and unused according to section 8.4.1.4. Treatment compliance will be summarized and listed for the safety analysis population using descriptive statistics. Non-compliance is defined as taking $< 80\%$ or $> 120\%$ of study medication during evaluation periods. The proportions of subjects with non-compliance as defined above will be summarized and listed for the safety analysis population.

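### The non-compliance limits are set per visit interval, but the only compliance formula pools all 24 cycles, so subjects outside the limits in single intervals are classed as compliant

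*SAP*

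**What the plan says.** **The rule.** Protocol 14.3: "Non-compliance is defined as taking <80% or >120% of study medication during evaluation periods (visit to visit".

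**The planned output.** SAP 9.1.6 repeats the two limits for the percentage "of study medication during evaluation periods" without the visit-to-visit qualifier, and does not define the period. It refers the calculation to SAP 8.4.1.4 and asks for the proportion of non-compliant subjects in the safety population.

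**The formula.** SAP 8.4.1.4 opens with "Treatment compliance during MT-1186-A03 will be calculated for each subject using the following". Numerator and denominator are both sums over cycles 1 to 24. The numerator takes planned days, subtracts missed days and adds the "count of additional study medication days taken in cycle i". On the planned number: "The #count of planned study medication dosing is 10 in cycle 1 to 24". On the source data: "The #count of study medication missed and additional study medication are collected by CRF visit". The section closes with "Treatment compliance will be calculated using the formula above and reported to 1dp".

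**Declared changes.** SAP section 11 lists one departure from the protocol, on physical examinations. Compliance is not mentioned. SAP section 2 gives the SAP's statistical details precedence over the protocol's.

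**The concern.** The rule and the formula work at different levels. A programmer who follows 9.1.6 to 8.4.1.4 finds a single whole-study percentage and will apply 80% and 120% to it. Nothing in the SAP says how to form an interval percentage, or how seven interval results become one label per subject.

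A whole-study ratio averages over time. A long gap in dosing, or a run of extra dosing days, is diluted by the other cycles. Extra days in one interval can also cancel missed days in another. The study exists to describe long-term safety on a fixed intermittent regimen, so the table that counts subjects off that regimen should count them by the protocol's definition.

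**Working it through.** The documents report no compliance result, so there is no figure of the plan's own to reproduce. The check applies the SAP formula and the protocol rule to the same dosing patterns.

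**Inputs**
- Planned dosing days: 10 per cycle in 24 cycles (SAP 8.4.1.4), so 24 × 10 = 240.
- Cycle length: 28 days (SAP 4.1), so 12 weeks = 3 cycles = 30 planned days.
- Visit intervals: protocol Table 1 has visits at Day 1 and Weeks 12, 24, 36, 48, 60 and 72 (cycles 1, 4, 7, 10, 13, 16 and 19), and the next in cycle 24. That gives six intervals of 30 planned days (cycles 1–18) and a last one of 60 (cycles 19–24): 6 × 30 + 60 = 240.
- Limits: below 80% or above 120%.

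**Formulas**, with M missed and A additional days
- Pooled (SAP 8.4.1.4): 100 × (240 − M + A) / 240.
- Interval k with n_k planned days: 100 × (n_k − m_k + a_k) / n_k.

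The pooled figure is the average of the interval figures weighted by n_k, so one interval moves it only by that interval's share (30/240 = 12.5% or 60/240 = 25%).

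| Pattern (all 24 cycles) | By interval | Pooled | Pooled label |
|---|---|---|---|
| One 12-week interval wholly missed | 0/30 = 0% | 210/240 = 87.5% | compliant |
| 7 of 30 missed in each of the six 12-week intervals | 23/30 = 76.7%, six times | (240 − 42)/240 = 198/240 = 82.5% | compliant |
| 14 dosing days in each of 3 cycles | 42/30 = 140% | (240 + 12)/240 = 252/240 = 105.0% | compliant |
| One 12-week interval missed, 30 extra days elsewhere | 0% in that interval | (240 − 30 + 30)/240 = 100.0% | compliant |
| Two 12-week intervals missed, 12 extra days elsewhere | 0%, twice | (240 − 60 + 12)/240 = 80.0% | compliant |
| Two 12-week intervals missed, no extra days | 0%, twice | 180/240 = 75.0% | non-compliant |
| Last interval wholly missed | 0/60 = 0% | 180/240 = 75.0% | non-compliant |
| 48 of 60 missed in the last interval | 12/60 = 20% | 192/240 = 80.0% | compliant |

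**Thresholds of the pooled rule.** With no extra days, 48 missed days give exactly 80.0% and are not flagged; 49 give 191/240 = 79.6% and are. With none missed, 48 extra days give 288/240 = 120.0% and are not flagged; 49 give 289/240 = 120.4% and are.

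**Two separate mechanisms.** The first three rows need no netting across intervals; pooling alone produces them. Netting is a further effect, seen in rows four and five.

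**Sensitivity to the choice of interval.** If the periods were instead the gaps between SAP analysis visits (Weeks 12, 24, 48, 72 and 96), the last three would have 60 planned days each. Wholly missing one would then be flagged (75.0%). Missing half of one would be 30/60 = 50% in the interval but 87.5% pooled, so the mismatch remains.

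**The case against.** **The information is not lost.** SAP 9.1.6 also summarises and lists exposure days for each cycle. A missed 12-week interval appears there as three cycles with zero days. This stands. A reader might infer from the formula that dosing gaps vanish from the report; the documents do not support that. What goes wrong is the classification.

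**Additional days belong in the numerator.** Without them no percentage could exceed 100%, and the 120% limit would be empty. This also stands. It is tempting to call the added term an error, but the fault is letting it offset missed days across intervals.

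**9.1.6 could be read as a per-interval rule, with 8.4.1.4 serving only the continuous summary.** The retained reference to evaluation periods allows that reading. But 9.1.6 names 8.4.1.4 as the source, and no interval ratio or combining rule exists. Equally, the SAP's precedence could make whole-study compliance a deliberate choice, but section 11 does not declare it.

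**The extreme patterns should be rare.** Protocol 9.6 has a withdrawal criterion for missed doses over two consecutive cycles, applied after consultation, and protocol 15.11 makes dosing beyond the specified amount or frequency an adverse event. Both limit frequency; neither changes how the table is computed. The pattern of 30 missed and 30 extra days illustrates the mechanism and is not a forecast.

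**No document says that one failing interval makes a subject non-compliant.** Correct. Under that rule, a single interval with 7 of 30 doses missed labels a subject who took 233/240 = 97.1% overall. The combining rule is the sponsor's choice, but it must be stated.

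**Conclusion.** The point holds as a conflict between the protocol's visit-to-visit definition and the formula the SAP uses to apply it. Followed as written, the SAP classes as compliant a subject at 0% in one 12-week interval (87.5% pooled), at 76.7% in all six 12-week intervals (82.5%), or at 140% in one (105.0%).

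The figures assume a subject with all 24 cycles and intervals that follow protocol Table 1. The wholly-missed example fails for the last interval, which is flagged at 75.0%. For subjects who stop early, the literal denominator of 240 could push the percentage down instead; that is a related gap which these figures do not cover.

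The consequence is limited to the descriptive non-compliance table. A reader might infer that the safety conclusions or the efficacy model are affected. They are not: compliance defines no analysis set (SAP section 6) and enters no model (SAP 9.2.1.1), no hypothesis is tested (SAP 7.2), and adverse event rates use exposure days, not the compliance percentage.

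**What to change.** In SAP 8.4.1.4 and 9.1.6:

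1. Define the evaluation period as the visit-to-visit interval of protocol 14.3, and compute compliance in each interval from the by-visit CRF counts, with that interval's planned doses as denominator.
2. Apply the lower and upper limits to each interval, and report the number and percentage of subjects outside them by interval.
3. State in advance how intervals combine at subject level, for example the number of subjects with at least one non-compliant interval.
4. Show missed and additional days in separate rows, because netting can still occur within an interval.
5. Keep the whole-study percentage as a secondary summary.

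The cost is some SAP wording and one extra derivation; no new data are needed. The reported non-compliance rate is likely to rise. Under the at-least-one-interval rule it cannot fall among subjects with all 24 cycles: the pooled figure is a weighted average of the interval figures, so whenever it lies outside a limit at least one interval does too. The table footnote should say which rule was used. If the sponsor prefers whole-study compliance as the classification, the alternative is to list that in SAP section 11 as a change from the protocol, with a reason.

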8.4.2. Efficacy Measures

Unless otherwise specified, the efficacy outcomes observed during MT-1186-A03 will be analyzed.

8.4.2.1. ALSFRS-R Total score

ALSFRS-R is a questionnaire used to measure the impact of ALS that is evaluated by the Investigator. The scale measures the subjects' physical function across 12 activities of daily living. The date of the evaluation along with the results will be recorded on the eCRF with respect to "4 Handwriting" and "5 eating motion," the results for the dominant hand (the hand used in daily life at the time of screening) will be recorded.

- ALSFRS-R total score will be derived from the sum of 12 items⁴. For the item 5 "Eating disorder," either the item (a) or (b) will be selected corresponding to subjects without or with gastrostomy respectively. The maximum total core is $4 \times 12 = 48$. If there is missing score data in an item, ALSFRS-R total score will be missing.
- ALSFRS-R domains Score
 - Bulbar function = total of items 1 to 3
 - Limb function = total of items 4 to 9
 - Fine motor function = total of items 4 to 6
 - Gross motor function = total of items 7 to 9
 - Respiratory function = total of items 10 to 12

If there is missing score data in an item, the corresponding domain score will be missing.

8.4.2.2. Time to death, tracheostomy, or permanent assisted mechanical ventilation:

The time to first occurrence of death, tracheostomy, or permanent assisted mechanical ventilation (defined on EMA Guideline on clinical investigation of medicinal products for the treatment of amyotrophic lateral sclerosis, 1 November 2015) will be derived as follow:

- In case the event mentioned above is observed any time from MT-1186-A01 first date of study drug, up to the last observed visit date, then the time variable for each subject will be calculated as:
 - The date of the event - First date of study drug in MT-1186-A01 +1
- In case the event mentioned above is **not** observed any time up to the last observed visit date, a right censoring will be performed for each subject at the last observed date regardless of treatment status. the time variable for each subject will be calculated as:
 - Last observed Date - First date of study drug in MT-1186-A01 +1

⁴ Refer to Appendix I of the protocol.

- Indicator (censoring) variable will be created to indicate an event (0) if the event was observed or censoring (1) if the event was not observed and at week 96 database lock the subjects was either discontinued or completed.

8.4.3. Safety Measures

Unless otherwise specified, the safety outcomes observed during MT-1186-A03 will be analyzed.

8.4.3.1. Adverse Events

An AE is any untoward medical occurrence in a subject or clinical investigation subject administered a pharmaceutical product that does not necessarily have a causal relationship with this IMP. An AE can therefore be any unfavorable and unintended sign (including an abnormal laboratory finding, for example), symptom, or disease temporally associated with the use of an IMP, whether or not considered related to the IMP.

Adverse events will be coded according to the MedDRA version 23.0.

AEs will be classified for Treatment Emergent AEs (TEAEs) if at least one of the following conditions is met:

- AE that was not present before the first dose in the MT-1186-A01 study but newly starts after administration of the first dose of study drug in the current study, or,
- AE that was present before the first dose in the MT-1186-A01 study but increased in severity following administration of the first dose of study drug in the current study.

- **Handling Partial Dates:**

Events with a missing start time, but with a start date equal to the date of first dose of study treatment in the current study will be considered treatment-emergent.

If the AE start date is incomplete, it will be imputed as follows for the purpose of determining TEAE, AE duration and AE Onset Cycle:

- If the start date is completely missing, the start date will be equal to the date of the first dose date of study treatment in the current study. However, if the stop date is not missing and is before the date of the first dose of study treatment, then the stop date will be used instead and the AE will not be considered as TEAE.
- If the start day is missing, but the month and year are not missing and are equal to the month and year of the first study dose in the current study, then

this event will be considered as TEAE.

- If the start day and month are missing, then the first day of the first month (January) will be used.

If an AE stop date is incomplete, it will be imputed as follows for the purpose of determining AE duration:

- If the AE stop date is completely missing, then the stop date will be equal to the subject's last observed date.
- If the Stop day is missing, but the month and year are not missing and are equal to the month and year of the last observed date, then stop date will be equal to last observed date.
- If the start day and month are missing, then the first day of the first month (January) will be used.

AEs will be classified for ADR if an AE is evaluated as having causally related to the investigational product with “a reasonable possibility”

Serious Adverse Events

A SAE is defined as any untoward medical occurrence that at any dose:

- Results in death;
- Is life-threatening;
- Requires hospitalization or prolongation of existing hospitalization;
- Results in persistent or significant disability or incapacity;
- Is a congenital anomaly or birth defect;
- Is an important medical event;

All SAEs occurring from the time written ICF is obtained from a subject until the end of the Safety Follow-up period or the withdrawal of the subject from the study must be reported to the Sponsor/CRO. All SAEs must also be entered in the AE section of the eCRF within 24 hours.

Duration of Adverse Events

Duration of the AE and time to the AE occurrence from Day 1 will be calculated and presented in days

Duration = AE stop date – AE start date + 1

Time to AE occurrence = AE start date – Day1 + 1.

Definition of Oral subgroup and PEG subgroup

The patients start with oral administration or PEG administration. The former can switch from oral administration to PEG/RIG dosing based the patient's disease progresses. Therefore, if the subject started with PEG/RIG or switched from oral dosing to receiving study medication through PEG/RIG during MT-1186-A01 or MT-1186-A03, then the subjects will be classified to PEG subgroup. Otherwise, the subjects will be classified as Oral subgroup.

If a switch date is incomplete and the switch day is missing, then the 15th day will be used.

Definition of TEAE under Oral dosing and PEG dosing

If the subjects have the date subject switched to PEG/RIG dosing during MT-1186-A01 or MT-1186-A03, TEAEs after the switched date will be defined as TEAEs under PEG dosing. Otherwise TEAEs will be defined as TEAEs under Oral dosing.

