#### **17.3.5.3 Safety Analyses**

An AE will be considered a treatment-emergent adverse event (TEAE) if

1. AE that was not present before the first dose in the MT-1186-A01 study but starts after administration of the first dose of study drug in the current study, or
2. AE that started after the first dose in the MT-1186-A01 and is ongoing in the current study, or
3. AE that was present before the first dose in the MT-1186-A01 study but increased in severity following administration of the first dose of study drug in the current study.

TEAEs will be coded using the latest available version of the MedDRA and will be summarized in incidence tables by SOC and PT. The numbers and proportions of subjects with TEAEs will be calculated by SOC and PT. The following summaries will be presented:

- TEAEs by SOC and PT
- TEAEs by SOC, PT, and severity
- TEAEs by SOC, PT, and drug relationship

- TEAEs leading to discontinuation of study drug by SOC and PT
- TEAEs leading to death by SOC and PT
- TEAEs related to study drug by SOC and PT
- TEAEs related to study drug by SOC, PT, and severity
- Serious TEAEs by SOC and PT
- Serious TEAEs related to study drug by SOC and PT

For each of the summaries, multiple occurrences of the same event within a subject will be counted once in the summaries by SOC and PT; multiple occurrences of the same event within a subject will be counted once in the maximum severity category (severe > moderate > mild) and/or maximum study drug relationship category (reasonable possibility/no reasonable possibility). If severity or relationship is found to be missing the most severe occurrence will be imputed for that particular summary.

All AEs for each subject, including multiple occurrences of the same event, will be presented in a full comprehensive listing including subject number, severity, seriousness, action taken, outcome, relationship to treatment, onset/stop date and duration.

Duration of the AE and time to the AE occurrence from start of oral edaravone will be calculated and presented in days (duration = AE stop date – AE start date + 1 and time to AE occurrence = AE start date – The first administration date of study drug + 1).

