9.3.1. Adverse Events

AEs that occurred on or after the first dose in the MT-1186-A03 will be summarized, which implies AE that occurred during MT-1186-A01 will not be summarized.

The following summaries will be provided:

- A Summary table of the overall incidence (number and percentage) and the number of events will be provided for TEAE, TEAE related to study drug, severe TEAEs, TESAEs, TEAEs leading to study treatment discontinuation and TEAEs leading to death.

The numbers and proportions of subjects will be calculated for the following:

- TEAEs by SOC and PT
- TEAEs by SOC, PT and severity
- Most Common ($\geq 5\%$ of patients) TEAEs by SOC and PT
- TEAEs related to study drug by SOC and PT
- TEAEs related to study drug by SOC, PT and severity
- TESAEs by SOC and PT
- TESAEs related to study drug by SOC and PT
- Severe TEAEs by SOC and PT
- Severe TEAEs related to study drug by SOC and PT
- TEAEs leading to study treatment discontinuation by SOC and PT
- TEAEs by SOC, PT and relationship to study drug
- TESAEs by SOC, PT and relationship to study drug
- TEAEs leading to death by SOC and PT

For these tables, SOC will be sorted by International Agreed Order; then within SOC, PT will be sorted by PT code.

The following summaries will be provided:

- A Summary table of the overall incidence (number and percentage) will be provided for Peripheral Neuropathy Standardized MedDRA query (SMQ) TEAEs

The numbers and proportions of subjects will be calculated for the following:

- TEAEs of Peripheral Neuropathy SMQ by SOC and PT
- Serious TEAEs of Peripheral Neuropathy SMQ by SOC and PT

TEAEs by Oral/PEG subgroup, SOC and PT

The numbers and proportions of subjects with TEAEs and event rate of TEAEs will be calculated by Oral/PEG subgroup, SOC and PT. The event rate of TEAEs will be calculated as the number of TEAEs divided by total exposure to investigational product by Oral/PEG dosing and expressed as 100 person years. Any TEAE occurred after subject switched to PEG will be classified under the PEG subgroup.

The exposure (in days) under Oral in cycle switched to PEG will be calculated as difference: Oral days=PEG switch Date during MT-1186-A01 or MT-1186-A03 - Cycle first date. If Oral days is less than 0 then Oral days will be 0.

The oral days does not exceed actual exposure duration (days) in the cycle. The exposure under PEG will be calculated as difference:

PEG days= actual exposure duration - Oral days.

TEAEs by Cycle

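### The SAP's TEAE definition omits adverse events that began in A01 and worsen only in severity in A03, and its defaults for incomplete onset dates are inconsistent

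*SAP*

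**What the plan says.** **Definition.** SAP 8.4.3.1 classes an event as a TEAE if it meets either of two conditions, each tied to the first study drug dose in A03:

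- "AE that was not present before the first dose in the MT-1186-A01 study but newly starts after administration of the first dose" (new start in A03);
- "AE that was present before the first dose in the MT-1186-A01 study but increased in severity following administration of the first dose" (older event that worsens).

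Protocol 17.3.5.3 has the same two categories and one more between them: "AE that started after the first dose in the MT-1186-A01 and is ongoing in the current study". The SAP omits it. SAP Section 2 says that the SAP's analysis text prevails over the protocol's. SAP Section 11, which lists changes from the protocol, mentions only physical examinations.

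**Scope.** SAP 8.4.3 states: "Unless otherwise specified, the safety outcomes observed during MT-1186-A03 will be analyzed". SAP 9.3.1 limits the summaries to events on or after the first A03 dose, "which implies AE that occurred during MT-1186-A01 will not be summarized".

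**Incomplete onset dates.** Where the start date is incomplete, "it will be imputed as follows for the purpose of determining TEAE, AE duration and AE Onset Cycle". The rules are:

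- Fully missing: "If the start date is completely missing, the start date will be equal to the date of the first dose date of study treatment" in A03, unless a known stop date is earlier.
- Day missing, month and year equal to those of first A03 dose: TEAE.
- Day and month missing: "If the start day and month are missing, then the first day of the first month (January) will be used". There is no stop-date check and no exception for the entry year.

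The January start-date line appears again in the list of stop-date rules.

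**The concern.** Long-term safety is the primary objective, and TEAE incidence and severity are named in the primary safety endpoints (protocol 7.2.1). Every subject enters A03 from A01, so an event that began on drug in A01 and became more severe on continued drug is one that an extension study is well placed to show. The SAP counts A03 worsening for an event that predates A01 but not for one that began in A01. Nothing in the text explains this difference.

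On dates, knowing the year of onset reverses the default that applies when nothing is known. An event that truly started in A03 can leave the TEAE tables because the site recorded more information.

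**Working it through.** The plan states no figure on this point, so the check runs the written rules over each kind of event.

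**1. Definition.** Inputs: protocol 17.3.5.3 categories 1 to 3, the two SAP 8.4.3.1 conditions, and the wording proposed under the fix.

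| Event | Protocol | SAP | Proposed |
|---|---|---|---|
| Onset before A01, unchanged in A03 | no | no | no |
| Onset before A01, more severe in A03 | TEAE | TEAE | TEAE |
| Onset in A01, ongoing, unchanged in A03 | TEAE | no | no |
| Onset in A01, ongoing, more severe in A03 | TEAE | **no** | TEAE |
| Onset in A03 | TEAE | TEAE | TEAE |

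Protocol and SAP differ in two rows. The third row follows from the scope stated in SAP 9.3.1. The fourth is the gap: the event did not newly start in A03, so it fails the first condition, and it was not present before A01, so it fails the second. The general TEAE wording in protocol Section 15 would count it on either reading of predose: it arose after study drug, or it worsened after dosing.

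**2. Would re-recording close the gap?** Protocol 15.1 makes a new adverse event of aggravation in seriousness, and protocol 15.3 says that serious and severe are different things. Protocol 15.6 lets a pre-existing illness become an adverse event if it worsens, but gives no onset date for severity-only worsening of a continuing event. The fields that it lists include severity and onset date but no date of severity change.

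**3. Onset-date defaults.** Take an event that truly starts in A03, in the calendar year of first A03 dose.

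| What is known of onset | Result under SAP |
|---|---|
| Nothing | set to first A03 dose: TEAE, unless stop date is earlier |
| Month and year, entry month | TEAE |
| Month and year, later month | TEAE from the month alone (no imputation line) |
| Year only | set to 1 January: non-TEAE unless first dose was on 1 January |

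A year-only onset in a later year is still a TEAE, because 1 January of that year falls after first dose.

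Illustration (dates assumed): first A03 dose 15 March 2021, event stop 10 September 2021. Duration = stop − start + 1.

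- Onset recorded as 2021: start 1 January 2021, non-TEAE, duration 253 days.
- Onset not recorded: start 15 March 2021, TEAE, duration 180 days.

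**4. How often the year-only default would be wrong.** No counts are given. Assume onset is uniform over the entry year. The share of wrong defaults is then the share of that year on or after first dose: (31 December − first dose + 1) / days in year.

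| Assumed first A03 dose | Share of entry year on or after it |
|---|---|
| 1 Nov 2020 | 61/366 = 17% |
| 15 Jan 2021 | 351/365 = 96% |
| 15 Mar 2021 | 292/365 = 80% |
| 15 Jun 2021 | 200/365 = 55% |
| 15 Sep 2021 | 108/365 = 30% |
| 15 Nov 2021 | 47/365 = 13% |

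The protocol synopsis estimates first enrolment in November 2020. For entrants late in a year, the non-TEAE default is therefore right more often than wrong. For entrants early in 2021 it is the reverse.

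**The case against.** The strongest reply is that leaving out A01 events is deliberate. SAP 9.3.1 says so openly and draws no line between unchanged and worsened events. That stands as an account of scope, and it means that a change to the definition alone would contradict 9.3.1. It does not explain why worsening of a still older event counts.

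A second reply is that sites may record worsening as a fresh A03 event. SAP 8.4.3.6, for example, sends significant examination abnormalities that start after consent to the adverse event form. The case report form and its completion guidelines would settle this, and the documents do not include them. So the wording gap is certain, while actual misclassification is not.

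A third is that the effect is narrow. Aggravation in seriousness is a new event, SAP 7.1 puts all data in listings, protocol 17.3.5.3 requires a full event listing, and the study is single-arm and descriptive. This stands: what can be lost is severity-only worsening of a continuing record, and it is lost from tables, not from the data. Year-only onsets should also be few, since onset date is a listed field and protocol Section 16 requires missing data to be explained and clarified with sites.

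Three stronger readings are tempting and are not supported. A reader might infer that the date rules contradict each other; they cover separate patterns and only their defaults disagree. A reader might infer that TEAEs are undercounted overall; the fully missing and entry-month rules can also move an event from before A03 into the TEAE tables. A reader might infer that the protocol category was dropped silently; the scope is stated in SAP 8.4.3 and 9.3.1, and only the Section 11 entry is absent.

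**Conclusion.** The point holds as a fault of wording that should be fixed before lock. By the literal text, an event that began in A01, is ongoing at A03 entry and increases in severity only is not a TEAE, while a pre-A01 event that does the same is. It would then appear only in listings. The start-date defaults are also inconsistent for year-only onsets in the entry year.

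The size cannot be given: the documents contain no counts of worsened A01-onset events or of incomplete onset dates, and the net direction over all the date rules is unknown. The shares above rest on assumed entry dates and uniform onset. Confidence is high on the wording gap and moderate on its effect on results, which depends on how sites recorded worsening.

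**What to change.** 1. Extend the second TEAE condition to any adverse event present before the first A03 dose, including A01 onset, that increases in severity after it. Amend the SAP 9.3.1 sentence so that only A01 events that do not worsen in A03 are left out. Where one record simply continues, compare its last A01 severity with its maximum A03 severity; list the events for which worsening cannot be derived.
2. For a year-only onset in the A03 entry year, use the A03 first dose date unless the stop date is earlier or the A01 record, linked by the retained Subject Identifier (protocol 14.4), shows that the event was already present.
3. Record in SAP Section 11 that the protocol's category for ongoing A01 events is removed for those that are unchanged. Restoring it is not needed.
4. Minor, adverse event duration only: replace the repeated January line in the stop-date list with the last day of the known month or year, capped at the last observed date. SAP 8.4.1.3 already uses end-of-month and end-of-year stop dates for medications.

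SAP Section 2 allows updates until final database lock. The cost is more than wording. SAP 8.4.1.1 already reports an outcome of the data review meeting, and linking A01 and A03 records takes programming and data review. TEAE counts may rise slightly, and some onsets before A03 may be counted; the check against A01 records limits this.
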